**6.4 Visit 6 (EOT1) Day 28±2; Week 4**

Visit 6 will consist of ADHD-RS with prompts, Barkley SCT Scale, BRIEF-A, Barkley Functional Impairment Scale (BFIS), neuropsychological battery, CGI, vital signs, assessment of adverse events (AE) and concomitant medications (CM). Study Medication is dispensed. Drug accountability performed. Patient will receive *two* study medication bottles.

**6.5 Telephone Visit- Day 35±2; Week 5**

Study Coordinator will call the patient to ask about safety and compliance. We will ask them; how had they been feeling since their last visit. We will document any adverse events, concomitant medications and medication compliance. Study coordinator will go over instructions regarding study medication and remind patient of their next appointment.

**6.6 Visit 7 (Baseline 2) Day 42±2; Week 6**

Visit 7 will consist of ADHD-RS with prompts, Barkley SCT Scale, BRIEF-A, Barkley Functional Impairment Scale (BFIS), neuropsychological battery, CGI, vital signs, assessment of adverse events (AE) and concomitant medications (CM). Study Medication is dispensed. Drug accountability is performed.

**6.7 Visits 8, 9, & 10 (Treatment) Day 49±2, Day 56±2, and Day 63±2; Weeks 7-9**

Visits 8 through 10 will consist of the ADHD-RS with prompts, Barkley SCT Scale, CGI, vital signs, assessment of adverse events (AE) and concomitant medications (CM). Study Medication is dispensed. Drug accountability is performed.

CONFIDENTIAL

## **6.8 Visit 11 End of Treatment 2; Day 70±2 Week 10**

End of treatment will consist of ADHD-RS with prompts, Barkley SCT Scale, BRIEF-A, Barkley Functional Impairment Scale (BFIS), C-SSRS, neuropsychological battery, CGI, vital signs, assessment of adverse events (AE) and concomitant medications (CM). Drug accountability is performed.

## **6.9 Follow-Up Telephone/End of Study- Visit Day 77±2; Week 11**

Study Coordinator will call the patient to ask how they been feeling since their last visit. We will document any adverse events, concomitant medications.

### **7.1 Sample Size Determination**

Phase I: Recruitment and Selection of SCT cases (Phenotype phase)

We plan to recruit 120 adults (20% screen fail rate) to evaluate at the screening visit; approximately 100 adults with ADHD at two sites (NYU and Mount Sinai) to identify 50 SCT+ and 50 SCT-. These patients will be evaluated with clinical measures of SCT (Barkley SCT Scale), ADHD (ADHD-RS with prompts), executive function (BRIEF- A), assessment of other psychiatric disorders (M.I.N.I) global impairment (CGI), functional impairment (FIRS- QS), suicidality (C-SSRS), and neuropsychological function (neuropsychological battery). Only patients in the SCT+ cohort will enter the treatment phase of the protocol.

Phase II: Treatment Phase

We are proposing a 2-site (NYU and Mount Sinai) study of LDX in 50 adults with

CONFIDENTIAL

ADHD + SCT. The study will be a double-blind, 10-week, cross-over treatment trial of LDX (4 weeks; 30 – 70 mg/day) vs. placebo (4 weeks) with an intervening single-blind placebo washout period (2 weeks). During the LDX treatment epoch, LDX treatment will be initiated at a dose of 30mg/day at Visit 2 and can be titrated up (in the judgment of the investigator) in increments of 20mg, based upon clinical response and tolerability, to 50mg/day at Visit 3 and 70mg/day at Visit 4. Subjects receiving daily doses of 50mg or 70mg of LDX will be allowed to down titrate one dosage step of 20mg during Visits 2-4 if (in the judgment of the investigator) they are having issues in tolerability. The highest effective dose of LDX will then be maintained until Visit 4. Patients will be seen weekly throughout the trial.

## 7.2 Statistical Methods

Phenotype Phase: Comparisons between the adult ADHD patients cohorts with SCT and without SCT in terms of ADHD symptoms (total, inattentive and hyperactive-impulsive, symptoms of executive function (BRIEF GEC, metacognition, behavioral regulation scales and subscales: Inhibit, Shift, Emotional Control, Initiate, Working Memory, Plan/Organize, Organization of Materials, Monitor), neuropsychological tests (CANTAB ADHD module, WAIS Coding and Symbol Search and Attention Network Test (ANT), and impairment (on Barkley Functional Impairment Scale (BFIS)) will be examine via One Way ANOVA .

Treatment Phase: Changes in outcome ratings in the patients in the treatment phase with LDX and placebo will be modeled with longitudinal generalized estimating equation (GEE) mixed regression models using STATA 12.0 [StataCorp, 2011 #25856] within the framework of the general linear model (GLM). The GLM allows us flexibility in modeling the outcome variable by choosing the appropriate distribution and link function. Each model will predict outcome scores from treatment group (drug vs. placebo), study visit (ordinal predictor), order (drug or placebo first) and the two and three-way interactions among: treatment group, visit, and order. We will first test for order effects and drop effects that are not significant at  $p < .05$ . The visit by treatment interaction indicates if the reduction in symptoms over time significantly differs between drug and placebo. Our primary analyses will be intention

CONFIDENTIAL

[SHIRE SCT s13-01288]  
Version: 03/03/2016

to treat (ITT) but we will explore the data with less conservative per protocol analyses to assure that we do not miss any signals in the data. Because this is a randomized trial, which follows subjects over a short period of time, missing data is not expected to impact our analyses. Should this become an issue, we will impute data using STATA's impute procedure. Using logistic regression, a responder analysis will be conducted using pre-hoc priori criteria for treatment response (30% decreases in total ADHD-RS and Barkley SCT scores). These will be last observation carried forward (LOCF) endpoint models that predict responder status (yes/no) from drug group, order and the drug by order interaction. Baseline symptom scores will be included as covariates.

Safety Analysis: Variables to be summarized and listed include vital signs, adverse events, clinical laboratory results, ECG readings, and the C-SSRS. All adverse events results will be tabulated in manuscripts along with significance testing using the appropriate general linear model. These models will use LOCF endpoint analyses with terms for drug, order and the drug by order interaction

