## 2 Study Objectives

Primary Objective: The primary objective is to examine changes in ratings of ADHD symptoms and SCT. The primary measure of ADHD symptoms will be the total score on the ADHD Rating Scale (ADHD-RS) with prompts [16]. The primary measure of SCT will be the Barkley SCT Scale.

Secondary Objectives:

- 1) Examine changes in the BRIEF-A Metacognition Index and Motivation Subscales as these subscales are more closely related to measures of arousal and motivation than other subscales of the BRIEF-A.
- 2) Examine changes in ratings of functional impairment via the B Barkley Functional Impairment Scale (BFIS).
- 3) Examine changes in a battery of neuropsychological tests of arousal and alerting, including:
  - i. The Cambridge Neuropsychological Testing Automated Battery (CANTAB) ADHD battery: A validated battery of 4 tests which assess motor speed (Motor Control Task), spatial working memory (Spatial Working Memory), response inhibition (Stop Signal Task), and sustained attention (Rapid Visual Information Processing) [17]. In addition, we have included the Attention Switching Task (AST), an useful test in defining the cognitive phenotype in individuals with ADHD + high IQ. Measures of reaction time and reaction time variability will be

CONFIDENTIAL

examined.

- ii. The Wechsler Adult Intelligence Scale-IV (WAIS-IV): Coding and Symbol Search subtests will be used to evaluate processing speed [18].
- 4) Examine potential differences in nature and severity of ADHD symptoms (total, inattentive, and hyperactive-impulsive), symptoms of executive function (BRIEF GEC, metacognition, behavioral regulation scales and subscales: Inhibit, Shift, Emotional Control, Initiate, Working Memory, Plan/Organize, Organization of Materials, Monitor), neuropsychological test performance on the CANTAB and WAIS subtests listed above, and impairment ( Barkley Functional Impairment Scale (BFIS)) [27]
- 5) The On-Top scale will be used on treatment outcome in adult ADHD to measure executive functions in daily life.[29][30]

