## **Study Phases**

### Recruitment and Selection of SCT cases (Phenotype phase)

We plan to recruit 120 adults (20% screen fail rate), to evaluate at the screening visit approximately 100 adults with ADHD at two sites (NYU and Mount Sinai) to identify 50 SCT+ and 50 SCT-. These patients will be evaluated with clinical measures of SCT (Barkley SCT Scale), ADHD (ADHD-RS with prompts), executive function (BRIEF-A), assessment of other psychiatric disorders (M.I.N.I.), global impairment (CGI), functional impairment (Barkley Functional Impairment Scale (BFIS)), suicidality (C-SSRS), and neuropsychological function (neuropsychological battery). Only patients in the SCT+ cohort will enter the treatment phase of the protocol.

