### **3.3 Secondary Study Endpoints**

The secondary study endpoints are to define the SCT phenotype and determine similarities and differences between adults with ADHD with and without SCT on SCT symptoms, executive function symptoms, nature and severity of ADHD symptoms, and neuropsychological profile

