## **4 Subject Selection and Withdrawal**

### **4.1 Inclusion Criteria**

- 1) Male or female between the ages of 18-60 of all races and ethnicity.
- 2) Meets DSM-IV-TR criteria for a primary diagnosis of inattentive or combined type ADHD as diagnosed via the Adult ADHD Clinician Diagnostic Scale version 1.2 (ACDS v1.2) [10].
- 3) If SCT+ group,  $\geq 5$  items on the Barkley SCT Scale must be rated 3 ("often") or 4 ("very often") and total SCT symptom score  $\geq 26$ ; must have a T-score  $\geq 65$  on the Metacognition Index Subscale of the Behavior Rating Inventory of Executive Function - Adult Version (BRIEF-A) [11].
- 4) If SCT+ group, Impairment: must have a total score  $> 95$ th percentile on the Barkley Functional Impairment Rating Screen (Barkley Functional Impairment Scale (BFIS) [13].
- 5) If SCT- group,  $< 5$  items on the Barkley SCT Scale must be rated 3 ("often") or 4 ("very often") and total SCT symptom score  $< 26$ ; must have a T-score  $< 65$  on the Metacognition Index and Motivation Subscales of the BRIEF-A.

CONFIDENTIAL

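### The phenotype ANOVA tests BRIEF-A Metacognition between cohorts selected on opposite sides of one Metacognition cut-off, so significance is built in; BFIS, gated in SCT+ only, is biased the same way by an unknown amount

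*Combined protocol and SAP*

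**What the plan says.** Section 4.1 sets the entry conditions for the two cohorts.

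- Item 3 (SCT+): besides the Barkley SCT Scale conditions, a T-score of 65 or more "on the Metacognition Index Subscale of the Behavior Rating Inventory of Executive Function - Adult Version (BRIEF-A").
- Item 4 (SCT+): a total score above the 95th "percentile on the Barkley Functional Impairment Rating Screen (Barkley Functional Impairment Scale (BFIS"). No matching condition is set for SCT-.
- Item 5 (SCT-): besides the opposite SCT Scale conditions, a T-score below 65 "on the Metacognition Index and Motivation Subscales of the BRIEF-A".

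Section 7.2 (Phenotype Phase) then compares these cohorts on ADHD symptoms, on "symptoms of executive function (BRIEF GEC, metacognition, behavioral regulation scales and subscales"), on neuropsychological tests, and finally states that "impairment (on Barkley Functional Impairment Scale (BFIS)) will be examine via One Way ANOVA".

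The comparison serves secondary objective 4 in section 2 ("Examine potential differences in nature and severity of ADHD symptoms (total, inattentive, and hyperactive-impulsive"), with a similar outcome list). It also serves the endpoint in section 3.3, which is to "determine similarities and differences between adults with ADHD with and without SCT on SCT symptoms, executive function symptoms" and other domains. Nothing in the document marks these tests as descriptive, leaves out the variables used for selection, or adjusts for selection.

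**The concern.** An outcome that also decides who enters which group cannot be tested between those groups. On Metacognition, the lowest SCT+ score must exceed the highest SCT- score whatever SCT does, so the entry rules alone produce the difference. A significant result could then be reported as evidence that SCT carries an executive-function deficit, which the design cannot show.

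BFIS has a milder form of the problem. The low end of the distribution is cut off in SCT+ and left in place in SCT-, so SCT+ looks more impaired even if SCT has no bearing on impairment.

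The other outcomes in section 7.2 (GEC, behavioral regulation, the subscales, ADHD symptoms, CANTAB, WAIS, ANT) are not entry criteria. Selection reaches them only through their correlation with the criteria. The Motivation subscale gated in item 5 is not named as an outcome in section 7.2. Section 3.3 does name SCT symptoms, which define the groups, as a compared outcome, although section 7.2 states no test for them.

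**Working it through.** The plan gives no effect size, power or error rate for this phase, so there is no stated figure to reproduce.

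**Inputs from the document.** The cut-offs in section 4.1; 50 SCT+ and 50 SCT- (section 7.1); one-way ANOVA, which for two groups is the t-test (section 7.2).

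**Assumptions.** Normal scores; a two-sided 5% level (section 3.1 states 0.05 for the treatment comparison only); SCT unrelated to every outcome, so any rejection is a false positive.

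**1. Metacognition, closed form.** Suppose the cut-off falls at the median.

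- Difference in means: 2 × 0.798 = 1.596 population SD.
- SD within each half: √(1 − 2/π) = 0.603.
- d = 1.596 / 0.603 ≈ 2.65.
- t ≈ 2.65 × √(50/2) ≈ 13.2, against a critical value of 1.98.

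**2. Metacognition, simulation.** The share above the Metacognition cut was 0.3, 0.5 or 0.7. The share above the BFIS cut was 0.3 to 0.99. The correlation between the two was 0, 0.3 or 0.5. That gives 54 settings of 4,000 trials each, 216,000 in all.

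- Rejection was 100% in every setting; the smallest t was 9.5.
- d, in within-group SDs, was 2.66–2.72 with BFIS independent and up to 3.0 at correlation 0.5.
- Adding the Motivation gate for SCT- gave d of 2.66–2.99 and still 100%.

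On the T-score scale, with means of 55–80 and SDs of 6–14 (18 settings), rejection was again 100%. The forced gap was 9.6 to 25.8 T points.

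**3. Does the p-value respond to a true link?** With mean 68 and SD 10:

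| SCT–Metacognition correlation | Mean gap (T points) | Rejection |
|---|---|---|
| 0 | 16.2 | 100% |
| 0.3 | 17.6 | 100% |
| 0.5 | 18.2 | 100% |

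Split on SCT alone, without the Metacognition gate, the same test rejects in 5.1%, 69% and 99% of trials.

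**4. BFIS.** If BFIS is independent of Metacognition and a share p of the recruited ADHD adults lies above the cut c, the shift in SCT+ is φ(c)/p population SDs. For p = 0.90, c = −1.282 and the shift is 0.1755/0.90 = 0.195 SD. False-positive rates:

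| Share above cut | Correlation 0 | Correlation 0.3 |
|---|---|---|
| 30% | 100% | 100% |
| 50% | 99.9% | 100% |
| 70% | 81–83% | 99.7–100% |
| 90% | 17–18% | 89–94% |
| 95% | 8–9% | 80–87% |
| 99% | 5% | 71–74% |

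At correlation 0.5 the rate is at least 99.4% throughout. If the Motivation gate is added and also correlates 0.3 with BFIS, the last three figures in the right-hand column become 94–100%, 87–99.9% and 81–99.5%.

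**5. Outcomes that are not entry criteria.** At correlation r with Metacognition and a median cut, the shift is 1.596 r. For r = 0.3 this is 0.479, the within-group SD is √(1 − 0.09 × 0.637) ≈ 0.97, so d ≈ 0.49, the expected t is about 2.5 and rejection is near 70%. Simulated rates:

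| r | 0 | 0.1 | 0.2 | 0.3 | 0.4 | 0.5 |
|---|---|---|---|---|---|---|
| Metacognition gate | 5% | 13–14% | 35–37% | 70–71% | 91–94% | 99% |
| With Motivation gate (correlated 0.6 with Metacognition) | 5% | 15–17% | 46–54% | 83–90% | 97–99% | 100% |

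**The case against.** Six points can be made for the plan.

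- **The cohorts may not be those of section 4.1.** Section 7.2 does not cite it, and a patient with, say, high SCT but Metacognition below 65 fits neither group. The document does not say whether such patients are analysed. This lowers certainty a little. But section 4.1 is the only operational definition of the groups, and the Study Summary and sections 3.1, 4.3 and 7.1 divide about 100 adults into 50 and 50 with no third group.
- **The gating reading and the analysed reading might differ.** The text places BRIEF-A and BFIS at the screening evaluation, whereas the schedule in section 6 shows one pre-treatment reading, at Visit 2. With a separate reading of reliability 0.9, 0.7 or 0.5, null rejection is still 100%, 100% and 99%.
- **The size of the Metacognition gap does carry a little information.** It moves from 16.2 to 18.2 T points, and the median p-value moves with it. That is correct, but significance does not change.
- **The BFIS bias has no fixed size.** This stands; it could be negligible. Section 3.3 also does not list impairment, so BFIS enters through objective 4 and section 7.2.
- **A caveat does not repair the tests on correlated outcomes such as GEC.** This also stands. The wording change limits what may be claimed from those tests; only a change to eligibility would make them valid.
- **The phase is exploratory and secondary, and one index among more than 15 outcomes is certainly affected.** This limits the weight. It does not make a p-value with a predetermined result worth reporting.

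**Conclusion.** The concern holds. For Metacognition, the planned ANOVA is significant whether or not SCT is related to it, so it cannot answer secondary objective 4. This rests on the section 7.2 cohorts being the section 4.1 groups and on roughly normal scores, and it held across every cut-off position and correlation examined.

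For BFIS the direction of the bias is certain and its size is not. The result depends on the share of recruited ADHD adults above the 95th percentile and on the correlation of BFIS with Metacognition, neither of which the document gives. The rates above show direction and range only.

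The damage is confined to objective 4 and the section 3.3 endpoint. "Only patients in the SCT+ cohort will enter the treatment phase of the protocol", so the randomized comparison takes place within SCT+ and is untouched. The point should be fixed, but it does not threaten the primary result.

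**What to change.** **Recommended: wording in section 7.2 only.**

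- State that Metacognition and BFIS are selection variables under section 4.1 and will be summarised by cohort without p-values.
- Treat the SCT-symptom comparison named in section 3.3 in the same way.
- State that differences in outcomes correlated with the entry criteria, GEC included, cannot be separated from selection. The other ANOVAs can stay with that caveat.

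This costs a few sentences. Eligibility, visits, sample size and the treatment phase do not change.

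**Optional: a design change, if these outcomes are to be tested against SCT.** Define the phenotype cohorts by the Barkley SCT Scale alone, or regress on the continuous SCT score. Section 4.1 must then also be amended so that the BRIEF-A and BFIS conditions apply only to treatment-phase entry and patients with mixed results stay in the phenotype sample. Item 5 plays no part in treatment entry. The 50/50 target in the Study Summary and sections 3.1, 4.3 and 7.1 would need revising. The drawbacks are unequal groups and a phenotype SCT+ group that differs from the treated one.

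Changing the analysis alone does not work. In the sample enrolled under section 4.1 as written, regrouping or regressing on SCT still rejects for Metacognition in 100% of runs, and regression for BFIS rejects in 12–100%. With the BRIEF-A and BFIS conditions removed from phenotype entry, all rates are 4.3–6.0%.

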### 3 Study Design

#### 3.1 General Design

- 1) Total number of subjects/Total sample size: Approximately 120 patients with ADHD (with the final number of subjects depending on the proportion of ADHD subjects who have SCT; we have based our projections on an estimated 50% prevalence) in the phenotype phase (screening visit); 50 adults with ADHD and SCT+ will enter the treatment phase with LDX and placebo. We will analyze data from all subjects who take at least one dose of medication in both blocks. Using a 20% drop-out rate to occur throughout the trial, we estimate that approximately 50 subjects will enroll in the trial; 46 patients will complete the first phase of treatment, 44 patients will complete the intervening placebo washout, and 40 patients will complete each treatment phase.
- 2) Justification for sample size: We will enroll a sufficient number of subjects to recruit 80 patients with ADHD and SCT to enter the treatment study. The 50% prevalence of SCT in adult ADHD has been established in community samples [1, 2]. Power for this study was calculated using PASS [22] based on the primary outcome, i.e. change between baseline and week 4 of treatment on the Barkley SCT scale. Previous studies suggest that the upper bound of the effect size for the comparison of ADHD

CONFIDENTIAL

medications vs. placebo for ADHD symptoms varies between 1.2 and 1.5 standard deviations. Using a conservative estimate of effect that is half as robust for SCT as ADHD we based on our calculations on a 0.6 ES for SCT symptoms. The primary comparison will be a reduction in SCT symptoms on LDX vs. placebo. With 45 evaluable patients with SCT we will have 80% power to detect an effect size (ES) of 0.6 using a two-sided test with a type I error of 0.05.

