### LDX Treatment Phase

We are proposing a 2-site (NYU and Mount Sinai) study of LDX in 50 adults with ADHD + SCT. The study will be a double-blind, 10-week, cross-over treatment trial of LDX (4 weeks; 30 – 70 mg/day) vs. placebo (4 weeks) with an intervening single-blind placebo washout period (2 weeks). During the LDX treatment epoch, LDX treatment will be initiated at a dose of 30mg/day at Visit 2 and can be titrated up (in the judgment of the investigator) in increments of 20mg, based upon clinical response and tolerability, to 50mg/day at Visit 1 and 70mg/day at Visit 3. Subjects receiving daily doses of 50mg or 70mg of LDX will be allowed to down titrate one dosage step of 20mg during Visits 3-5 if (in the judgment of the investigator) they are having issues in tolerability. The highest effective dose of LDX will then be maintained until Visit 6. Patients will be seen weekly throughout the trial except during placebo washout. The same schedule will occur during Phase 2 of the study.

CONFIDENTIAL

During the Phase 2 LDX treatment epoch, LDX treatment will be initiated at a dose of 30mg/day at Visit 7 and can be titrated up (in the judgment of the investigator) in increments of 20mg, based upon clinical response and tolerability, to 50mg/day at Visit 1 and 70mg/day at Visit 8. The titration procedure will follow that of phase 1.

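### A pre-test at p < .05 decides whether the order and drug-by-order terms stay in the primary crossover model; it says almost nothing about carry-over and leaves the meaning of the drug coefficient to the data

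*Combined protocol and SAP*

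**What the plan says.** Section 7.2 (Treatment Phase) models outcome scores by GEE from treatment group, "study visit (ordinal predictor), order (drug or placebo first) and the two and three-way interactions among: treatment group, visit, and order". It continues: "We will first test for order effects and drop effects that are not significant at" p < .05. No term is called period or carry-over. The section does not say how the LDX effect is to be read if an order term is kept.

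The design in section 3.1 (LDX Treatment Phase) is four weeks of LDX and four of placebo "with an intervening single-blind placebo washout period (2 weeks"). A second baseline follows the washout. Section 6.6 states: "Visit 7 will consist of ADHD-RS with prompts, Barkley SCT Scale, BRIEF-A". Section 3.1 (General Design) bases the power on "change between baseline and week 4 of treatment on the Barkley SCT scale". Section 5.3 specifies block randomisation to the starting treatment but gives no ratio.

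The responder models in section 7.2 and the adverse-event models after them list drug, order and drug-by-order, with no drop rule attached.

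**The concern.** Dropping a term because its test is not significant treats the effect as absent. For carry-over that inference is weak, because the contrast is between patients in a trial sized for a drug comparison.

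A period effect is plausible here. Section 4.1 requires an SCT score of at least 26 for the SCT+ group, and no such threshold is stated at Visit 7, so regression to the mean would fall mainly in block 1. The neuropsychological battery is also repeated, which allows practice gains. Whether the period contrast enters the model is nevertheless left to a significance test.

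The primary comparison of LDX with placebo is at stake: which model produces it, and what its drug coefficient means once drug-by-order is kept or dropped.

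**Working it through.** **1. The plan's own figure.** Section 3.1 states: "With 45 evaluable patients with SCT we will have 80% power to detect an effect size (ES) of 0.6". The level is two-sided 0.05. As a two-sample comparison with 45 per arm, z = 0.6/√(2/45) = 2.85 and power is Φ(2.85 − 1.96) ≈ 81%. A paired t-test on 45 patients with correlation 0 gives 79.5%. The figure reproduces on either reading. It does not reproduce with 45 in total over two arms (52%) or as a paired test with correlation 0.5 (97.6%). No power is stated for the order test. What follows uses only the 0.6 SD scale and the two-sided 0.05 level.

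**2. What the terms estimate.** Let τ be the drug effect, π the shift from block 1 to block 2, and λ the LDX carry-over into block 2.

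| Order | Block 1 | Block 2 | Total | LDX − placebo |
|---|---|---|---|---|
| LDX first | τ | π + λ | τ + π + λ | τ − π − λ |
| Placebo first | 0 | τ + π | τ + π | τ + π |

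- Order main effect (difference in totals): λ.
- Drug-by-order (half the difference in the last column): π + λ/2.
- Drug effect averaged over orders: τ − λ/2.

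The λ/2 is there whether or not order is in the model. In a simulation with 22 per order, correlation 0.5, τ = −0.60 and λ = −0.30, the drug estimate averaged −0.45. That was so both overall and in the runs where the order test was significant.

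**3. Power of the order test.** Inputs: 50 enter and "40 patients will complete each treatment phase" (section 3.1). Assumed: SD 1 per block, 1:1 orders, within-patient correlation ρ. SE = √(2(1 + ρ) × 4/N). For N = 50 and ρ = 0.5, SE = √(3 × 4/50) = 0.49 and z = 0.30/0.49 = 0.61, which gives 9.4%.

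| N | λ 0.30, ρ 0 | λ 0.30, ρ 0.5 | λ 0.30, ρ 0.8 | λ 0.60, ρ 0.5 |
|---|---|---|---|---|
| 40 | 10.3% | 8.5% | 7.9% | 19.5% |
| 45 | 11.0% | 8.9% | 8.3% | 21.3% |
| 50 | 11.7% | 9.4% | 8.6% | 23.2% |

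Adjusting totals for baseline raises the 0.30 SD figures to about 10 to 14% (ρ 0.3 to 0.7). For 80% power at N = 45 and ρ = 0.5, λ would have to be (1.96 + 0.84) × √(12/45) ≈ 1.45 SD. The shift in the drug effect would then be 0.72 SD, more than the whole planned 0.6.

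**4. Period.** This contrast is within patients and better powered. For π = 0.3 at N = 45 and ρ = 0.5, z = 0.6/√(4/45) = 2.01, so the term is kept about 52% of the time (47.5% at N = 40, 56% at N = 50). With balanced orders, dropping it leaves the drug estimate where it was. With n₁ LDX-first and n₂ placebo-first completers, the bias from dropping it is π(n₂ − n₁)/N:
- 18/22: 0.3 × 4/40 = 0.03 SD.
- 16/24: 0.3 × 8/40 = 0.06 SD.

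**5. Meaning of the drug coefficient.** With drug-by-order kept and 0/1 coding, the coefficient is the effect in the reference order, τ − π − λ or τ + π. Simulated with 50 patients, ρ = 0.5, a drug effect of −0.60 and a 0.3 SD period shift, it averaged −0.90. Centred coding gave −0.59, and so did dropping both order terms. With no drug effect, no carry-over, a 0.3 SD period shift and 40 to 50 patients, pre-testing and then reading the 0/1 coefficient rejected in about 25 to 30% of runs. The fixed contrast averaged over orders rejected in 5%.

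**6. Precision of direct looks at carry-over.** Visit 7 difference adjusted for Visit 2, with the 44 patients expected to finish washout and ρ = 0.5: SE = √(0.75 × 4/44) = 0.26, 95% CI half-width 0.51 SD, power 21% for 0.30 SD. Block 1 difference with the 46 expected to finish that block, adjusted likewise: half-width 1.96 × √(0.75 × 4/46) = 0.50 SD.

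These calculations use one summary score per block. The exact power of the planned GEE cannot be computed, because the working correlation and the coding of visit are not given.

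**The case against.** The best defence is that the design, not the test, deals with carry-over. There is a two-week placebo washout and a fresh baseline at Visit 7. The powered time point in block 2 is Visit 11 (day 70), six weeks after block 1 ends (day 28). The Study Summary's own screening washout for psychostimulants is one week. All of this stands.

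A reader might infer from a weak test that dropping order shifts the LDX effect by a quarter. The documents do not support that. The 25% is λ/2 = 0.15 SD against 0.6, for a carry-over of 0.30 SD chosen for illustration, and keeping the term would not remove it. Nor is the pre-test the plan's only safeguard, and nothing shows that carry-over exists. The direction of any bias also depends on the outcome form. On raw scores, persisting benefit shrinks the LDX effect. On change from block baseline, benefit still present at Visit 7 and gone by Visit 11 would enlarge it. Only the raw-score case is computed here.

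A second defence is that visit may absorb time. The schedule numbers visits uniquely across both blocks, and visit is not an order effect. If visit is coded study-wide, some of the period shift enters that way. The plan does not say whether visit is study-wide or within block, so this cannot be relied on.

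Finally, the supportive estimates proposed below are imprecise too, and keeping drug-by-order without naming a contrast could do harm. Both points are right and shape the fix.

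**Conclusion.** The concern holds as a fault in how the primary model is chosen. It is not a demonstrated bias. A non-significant order test cannot support the absence of carry-over: power is about 8 to 12% for 0.30 SD over correlations 0 to 0.8 and 40 to 50 patients, and about 20 to 23% for 0.60 SD at correlation 0.5, all assuming 1:1 orders and SD 1 per block. The rule makes the fitted model, and possibly the meaning of the drug coefficient, depend on the data. With balanced orders and an averaged contrast, the consequence for the LDX estimate is nil. With the modest imbalance shown it is 0.03 to 0.06 SD for a 0.3 SD period shift. It becomes serious only if drug-by-order is kept and a single-order coefficient is reported as the LDX effect, which the present wording does not prevent. This should be changed, since the remedy is nearly free.

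**What to change.** Replace the sentence in section 7.2 with text to this effect: *Treatment, period and sequence (order) are fixed terms in the primary model regardless of p value; no pre-test selects the model; the LDX effect, including treatment-by-visit at week 4, is the contrast averaged equally over the two orders.* State that visit means week within block. Name the same averaged contrast for the responder and adverse-event models, which already list drug-by-order.

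Add two supportive estimates with confidence intervals, not used as gates: the Visit 7 difference between orders adjusted for Visit 2, and the LDX–placebo difference in block 1 alone. Say in advance that both are imprecise (half-width about 0.5 SD), and rest the case against carry-over on the washout together with these estimates.

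Cost: one or two degrees of freedom, two extra estimates and SAP wording. No new data.
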